-1	is ≥25% less total GS-5829 administered over a 28 day period	6 subjects	If no DLT in 6 subjects at this dose level, then expand to maximum total of all Group 3 subjects of 40 (approx. 28 additional subjects)

Sites in France will be limited to Group 3 enrollment only.

Dose escalation in Group 1 will continue until identification of the MTD, or a suitable lower recommended dose, for Phase II studies. At least 6 subjects should be treated and evaluated at the GS-5829 dose level recommended for Phase II studies.

A DLT in Group 1 or 2 is a toxicity defined below considered possibly related to GS-5829 occurring during the DLT assessment window (Study Day 1 through C1D28) in each cohort.

- Grade ≥ 4 neutropenia (absolute neutrophil count [ANC] < 500/mm³)
- Grade ≥ 3 neutropenia (ANC < 1000/mm³) with fever (a single temperature of > 38.3°C or a sustained temperature of ≥ 38°C for more than one hour)
- Grade ≥ 3 thrombocytopenia
- Grade ≥ 2 bleeding (e.g. gastrointestinal, respiratory, epistaxis, purpura)
- Grade ≥ 3 or higher non-hematologic toxicity, except:
 - Grade 3 nausea or emesis with maximum duration of 48 hours on adequate medical therapy
 - Grade 3 diarrhea which persists for < 72 hours in the absence of maximal medical therapy
- Grade ≥ 2 non-hematologic treatment-emergent adverse event (TEAE) that in the opinion of the investigator is of potential clinical significance such that further dose escalation would expose subjects to unacceptable risk
- Treatment interruption of ≥ 7 days due to unresolved toxicity
- For certain toxicities such as laboratory assessments without a clear clinical correlate, a discussion between the Investigator and Medical Monitor may take place to determine if

this AE should be assessed as a DLT necessitating dose reduction. However, any Grade 3 or Grade 4 elevation in AST or ALT associated with a Grade 2 elevation in bilirubin that is at least possibly related to study drug will be considered a DLT.

Group 3: For the first 6 subjects enrolled in the aggressive lymphoma group (Group 3), a modification of the DLT assessment for hematologic toxicity will be:

- Grade ≥ 4 neutropenia (absolute neutrophil count [ANC] $< 500/\text{mm}^3$) which persist for > 3 days upon interruption of GS-5829 (administration of growth factors not allowed concurrently, but allowed during GS-5829 interruption)
- Grade ≥ 4 thrombocytopenia ($< 25,000/\text{mm}^3$)

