4.2. Inclusion Criteria

Subjects must meet all of the following inclusion criteria to be eligible for participation in this study.

- 1) Male or female ≥ 18 years of age. Subjects in Group 2 must be female.
- 2) Group 1: Histologically or cytologically confirmed advanced malignant solid tumor or lymphoma (any subtype) that is refractory to or intolerant of standard therapy or for which no standard therapy is available.
- 3) Group 2: Histologically or cytologically confirmed breast cancer with evidence of metastatic or locally advanced disease not amenable to resection or radiation therapy with curative intent and who have progressed during treatment with at least one prior hormonal therapy. Prior chemotherapy for advanced/metastatic disease is allowed.
 - a. Documentation of ER positive ($\geq 1\%$ positive stained cells by local standards) based on the most recent tumor biopsy, unless bone only disease.
 - b. HER2-negative tumor based on local testing on most recent tumor biopsy (immunohistochemistry score 0/1+ or negative by in situ hybridization HER2/CP17 ratio < 2 or for single probe assessment HER2 copy number < 4)
 - c. Post, pre or peri-menopausal subjects to be in the post-menopausal state as defined by one of the following:
 - i. Age ≥ 60 years
 - ii. Age < 60 years and cessation of regular menses for at least 12 consecutive months in the absence of chemotherapy, tamoxifen, toremifene, or ovarian suppression and serum estradiol and FSH level within the post-menopausal range
 - iii. Prior bilateral oophorectomy
 - iv. Pre/perimenopausal women can be enrolled if amenable to be treated with the LHRH agonist goserelin. Patients must have commenced treatment with goserelin or an alternative LHRH agonist at least 4 weeks prior to first dose of study drug. If patients have received an alternative LHRH agonist prior to study entry they must switch to goserelin for the duration of the study.

- 4) Group 3 lymphoma expansion: Subjects with lymphoma are limited to diffuse large B-cell lymphoma or peripheral T-cell lymphoma that are refractory to or intolerant of standard therapy or for which no standard therapy is available
- 5) All acute toxic effects of any prior antitumor therapy resolved to Grade ≤ 1 before the start of study drug dosing (with the exception of alopecia [Grade 1 or 2 permitted] and neurotoxicity [Grade 1 or 2 permitted])
- 6) ECOG Performance Status of ≤ 1
- 7) Life expectancy of > 3 months, in the opinion of the Investigator

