- 8) Adequate organ function defined as follows:
 - a. Hematologic: Platelets $\geq 100 \times 10^9/L$; Hemoglobin ≥ 9.0 g/dL; ANC $\geq 1.5 \times 10^9/L$ (without platelet transfusion or any growth factors within previous 7 days of the hematologic laboratory values obtained at screening visit). Patients in the Group 3 lymphoma expansion may be enrolled with an ANC of $\geq 1.0 \times 10^9/L$; Platelets $\geq 75 \times 10^9/L$.
 - b. Hepatic: Aspartate transaminase (AST) / Alanine transaminase (ALT) ≤ 2.5 x upper limit of normal (ULN) (if liver metastases are present, ≤ 5 x ULN); Total or conjugated bilirubin ≤ 1.5 x ULN
 - c. Renal: Serum Creatinine ≤ 1.5 x ULN or creatinine clearance (CrCl) ≥ 60 ml/min as calculated by the Cockcroft-Gault method
- 9) Coagulation: International Normalized Ratio (INR) ≤ 1.2
- 10) Negative serum pregnancy test for female subjects ([Appendix 7](#))
- 11) Male subjects and female subjects of childbearing potential who engage in heterosexual intercourse must agree to use protocol specified method(s) of contraception as described in [Appendix 7](#).
- 12) Females who are nursing must agree to discontinue nursing before the first dose of GS-5829
- 13) Able and willing to provide written informed consent to participate in the study

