6.7.1. GS-5829

For subjects without lymphoma, if at any time in the study a subject experiences a toxicity consistent with a Grade 4 DLT (see Section 3.2 for the definition of a DLT), GS-5829 treatment will be discontinued permanently, with the exception of Grade 4 neutropenia or thrombocytopenia. If a subject experiences Grade 4 neutropenia or thrombocytopenia or any other < Grade 4 toxicity consistent with a DLT (per Section 3.2), dosing with GS-5829 will be postponed until the toxicity is resolved to Grade 0 or 1 (as defined by the CTCAE, version 4.03) or returns to the subject's baseline value. If the toxicity resolves to Grade 0 or 1 or returns to the subject's baseline value within 28 days from the start of the event, the subject may resume dosing of GS-5829 at a dose that is at least one dose level lower after discussion with the Gilead Medical Monitor.

For subjects with lymphoma, if the toxicity is neutropenia or thrombocytopenia consistent with the definition of a DLT, the dose may be resumed at either one lower dose level, or the same dose with an alternative dosing schedule, which decreases the total amount of GS-5829 administered over a 28 day period to at least 25% less than the previous cohort (eg 14 days on and 7 days off). If the subject experiences a recurrence of a non-hematologic toxicity meeting criteria for DLT after restarting study drug at a lower dose or if the toxicity does not resolve within 28 days, treatment with GS-5829 will be discontinued. For subjects with lymphoma, if the recurrent toxicity is hematologic a second dose decrease is allowed (lowest dose allowed 1.0 mg) in either total daily dose or by a change in schedule such that the total amount of GS-5829 administered over a 28 day period is decreased by at least 25% after discussion with the Gilead Medical Monitor.

Table 6-2. Dose Reduction of GS-5829

NCI CTCAE Grade	Recommendation	
	Group 1 and 2: Non-lymphoma GS-5829	Group 3: Lymphoma GS-5829
HEMATOLOGICAL ADVERSE EVENTS		
Neutropenia		
Grade ≤ 3 Neutropenia	Maintain current dose level and schedule.	

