Grade 4 neutropenia (or occurrence of Grade ≥ 3 neutropenia (ANC < 1000/mm ³) with fever (a single temperature of > 38.3°C or a sustained temperature of ≥ 38°C for more than one hour) or infection	Hold dosing with GS-5829 until the toxicity is resolved to ≤ 1. If the toxicity resolves to ≤ 1 within 28 days, the subject may resume dosing of GS-5829 at a dose that is at least one dose level lower after discussion with the Gilead Medical Monitor. Granulocyte-colony Stimulating Factor (GCSF) is allowed	Hold dosing with GS-5829 until the toxicity is resolved to ≤ 1. If the toxicity resolves to ≤ 1 within 4 days, the subject may resume dosing of GS-5829 at the same dose or a dose lower. If recovery to grade ≤ 1 takes > 4 days, but within 28 days, then the subject may resume dosing of GS-5829 at a dose that is at least one dose level lower after discussion with the Gilead Medical Monitor. GCSF is allowed during dose interruption, but is not to be administered on the same day as GS-5829
Thrombocytopenia		
Grade ≤ 2 Thrombocytopenia	Maintain current dose level and schedule.	
Grade 3 Thrombocytopenia	Hold dosing with GS-5829 until the toxicity is resolved to ≤ 1. If the toxicity resolves to ≤ 1 within 28 days, the subject may resume dosing of GS-5829 at a dose that is at least one dose level lower after discussion with the Gilead Medical Monitor	Hold dosing with GS-5829 until the toxicity is resolved to ≤ 1. If the toxicity resolves within 7 days, the subject may either resume at the same dose or a dose with is one level lower or at an intermittent dosing schedule. If the toxicity takes > 7 days to resolve to ≤ Grade 1, then the drug must be resumed at a lower dose or an intermittent dosing schedule after discussion with the Gilead Medical Monitor
Grade 4 Thrombocytopenia	Hold dosing with GS-5829 until the toxicity is resolved to ≤ 1. If the toxicity resolves to ≤ 1 within 28 days, the subject may resume dosing of GS-5829 at a dose that is at least one dose level lower after discussion with the Gilead Medical Monitor. If it takes > 28 days, then GS-5829 will be permanently discontinued	Hold dosing with GS-5829 until the toxicity is resolved to ≤ 1 at which time the subject may either resume at a dose with is one level lower, or at intermittent dosing schedule (at least 25% less GS-5829 in a 28 day dosing period) after discussion with the Gilead Medical Monitor.

NCI CTCAE Grade	Recommendation	

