Appendix 6. Common Terminology Criteria for Adverse Events (CTCAE) v4.03

CTCAE v 4.03 can be accessed from the below link:

<http://www.hrc.govt.nz/sites/default/files/CTCAE%20manual%20-%20DMCC.pdf>

Appendix 7. Pregnancy Precautions, Definition for Female of Childbearing Potential, and Contraceptive Requirements

1) Definitions

a. Definition of Childbearing Potential

For the purposes of this study, a female born subject is considered of childbearing potential following the initiation of puberty (Tanner stage 2) until becoming post-menopausal, unless permanently sterile or with medically documented ovarian failure.

Except in Group 2, subjects with breast cancer who are also receiving hormonal therapies, women are considered to be in a postmenopausal state when they are ≥ 60 years of age with cessation of previously occurring menses for ≥ 12 months without an alternative cause. In addition, women of any age with amenorrhea of ≥ 12 months may also be considered postmenopausal if their follicle stimulating hormone (FSH) level is in the postmenopausal range and they are not using hormonal contraception or hormonal replacement therapy.

Permanent sterilization includes hysterectomy, bilateral oophorectomy, or bilateral salpingectomy in a female subject of any age.

In addition, Group 2 subjects (breast cancer) who are pre/perimenopausal women are considered in a postmenopausal state due to treatment with the LHRH agonist goserelin. Patients must have commenced treatment with goserelin or an alternative LHRH agonist at least 4 weeks prior to first dose of study drug, leading to a reduction in luteinizing hormone production and consequent reduction of sex steroid hormones to castration levels by the time of exposure to study drugs.

b. Definition of Male Fertility

For the purposes of this study, a male born subject is considered to be fertile after the initiation of puberty unless permanently sterile by bilateral orchidectomy or medical documentation.

2) Contraception Requirements for Female Subjects

a. Study Drug Effects on Pregnancy and Hormonal Contraception

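### Group 3 may enter at a neutrophil count that Table 6-2, read literally, does not accept as recovery, and Section 6.7.1 gives the return-to-baseline alternative only in a paragraph opening with non-lymphoma subjects

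*Protocol*

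**What the plan says.** **Entry.** Protocol Section 4.2, criterion 8a (also in the Synopsis), asks for an ANC of at least 1.5 × 10⁹/L, then relaxes this for one group: "Patients in the Group 3 lymphoma expansion may be enrolled with an ANC of" 1.0 × 10⁹/L or more. Criterion 5 adds a separate limit: "All acute toxic effects of any prior antitumor therapy resolved to Grade" 1 or better, with exceptions only for alopecia and neurotoxicity.

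**Grading.** Two ANC limits are printed. Section 3.2 gives "Grade ≥ 4 neutropenia (absolute neutrophil count [ANC] < 500/mm³", and Table 6-2 refers to "occurrence of Grade ≥ 3 neutropenia (ANC < 1000/mm ³) with fever". The Grade 1/2 limit is not printed. Appendix 6 says only "CTCAE v 4.03 can be accessed from the below link".

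**Resumption, table.** For Grade 4 or febrile neutropenia, the Group 3 column of Table 6-2 holds drug until Grade 1 or better. "If the toxicity resolves to ≤ 1 within 4 days, the subject may resume dosing" at the same or a lower dose; recovery after more than 4 but within 28 days means at least one level lower. Baseline is not mentioned, and the Group 1 and 2 cell does not mention it either.

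**Resumption, text.** Section 6.7.1 has a paragraph that opens with subjects without lymphoma. There dosing is "postponed until the toxicity is resolved to Grade 0 or 1" or back to the subject's own baseline. The lymphoma paragraph that follows states no recovery threshold.

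**DLT.** "Treatment interruption of ≥ 7 days due to unresolved toxicity" is an item in the Section 3.2 list introduced for Groups 1 and 2. For the first 6 Group 3 subjects the section announces a modification of the hematologic assessment. Its neutropenia item needs an ANC below 500/mm³ lasting more than 3 days after interruption. Nothing says whether the interruption item applies to Group 3.

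**The concern.** The lower entry limit exists only for Group 3, so Group 3 is where a subject can recover fully to the starting count and still fall short of Grade 1. On a literal reading, the alternative that would deal with this is attached to the subjects who enter at 1.5 or above.

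At stake are dose intensity and continued treatment for such a subject, and possibly the DLT count among the first 6, which decides whether Group 3 expands. Sites also have to choose between the table and the text, so two sites could manage the same count differently.

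**Working it through.** The plan states no figure on this point, so there is none to reproduce. The check is mainly a comparison of provisions.

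**Step 1: grade at the entry floor.** One litre is 10⁶ mm³, so 1.0 × 10⁹/L is 1000/mm³. The printed Grade 3 range is below 1000/mm³, so a count of exactly 1000 is outside Grade 3 and lies in the adjoining grade, Grade 2. How far Grade 2 extends upward cannot be read from the documents. If the Grade 1/2 limit is assumed to be 1.5 × 10⁹/L, the affected entry range is 1.0 to below 1.5. Any limit above 1.0 leaves some affected range.

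**Step 2: provisions side by side.**

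| Provision | Groups 1 and 2 | Group 3 |
|---|---|---|
| Entry ANC (4.2, 8a) | ≥ 1.5 × 10⁹/L | ≥ 1.0 × 10⁹/L |
| Table 6-2, recovery needed | Grade ≤ 1 | Grade ≤ 1 |
| Table 6-2, baseline alternative | none | none |
| 6.7.1 text, baseline alternative | given | not given on a literal reading |
| ≥ 7-day interruption as DLT (3.2) | listed | not stated |

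Text and table already disagree for Groups 1 and 2. For Group 3 the table is stricter than the entry criterion, and the text does not clearly relieve it.

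**Step 3: follow one subject.** A Group 3 subject enters at 1000/mm³, falls below 500/mm³, is held, and returns to 1000/mm³.

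- Under Table 6-2 the count is still Grade 2, so the hold continues.
- After 4 days the same-dose option has gone.
- At 28 days the table gives no route back. The lymphoma paragraph has a 28-day discontinuation clause, but its sentence opens with recurrent non-hematologic toxicity, so its application to a first hematologic event is uncertain.

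**Step 4: DLT routes.** The recovered count does not meet Group 3's own neutropenia DLT, because it is not below 500/mm³. The only route from the hold itself is the interruption item. That requires the item to carry over to Group 3, a subject at baseline to count as unresolved, and at least 7 days of hold to fall in the DLT window in one of the first 6 subjects.

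**Step 5: possible effect on the gate.** This is an illustration. Let p be the true DLT rate and e the chance that a subject without a true DLT is counted only because of the hold. The documents give neither. Then p′ = p + (1 − p)e, and with the Section 3.2 text rule (2 or more of 6),

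P(X ≥ 2) = 1 − (1 − p′)⁶ − 6p′(1 − p′)⁵.

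At p = 0.15:

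- e = 0: p′ = 0.15; P = 1 − 0.3771 − 0.3993 = 0.22
- e = 0.05: p′ = 0.15 + 0.85 × 0.05 = 0.1925; P = 1 − 0.2772 − 0.3965 = 0.33
- e = 0.10: p′ = 0.15 + 0.85 × 0.10 = 0.235; P = 1 − 0.2004 − 0.3694 = 0.43

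If the interruption item does not apply to Group 3, e = 0 and the probability stays at 0.22.

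**The case against.** **A stricter threshold after a severe event may be intended.** Resuming after Grade 4 or febrile neutropenia is not the same decision as enrolling, so a gap between the two limits is not in itself a contradiction. That is fair. Against it, Group 3's other hematologic rules are looser than those for Groups 1 and 2, and Table 6-2 accepts a return to baseline for interrupted lower-grade events that are neither hepatic nor hematologic. If the strictness is deliberate, the protocol does not say so.

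**The baseline clause may reach lymphoma subjects.** The non-lymphoma restriction opens only the first sentence of its paragraph, and the sentence with the baseline clause carries no restriction of its own. The table omits baseline even where the text grants it, so its silence for Group 3 is weak evidence. Section 6.7 also calls the rules guidelines. This shows that more than one reading is open; it does not make the passages agree.

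**Few subjects are affected.** Criterion 5 bars Grade 2 neutropenia left over from prior antitumor therapy, which leaves mainly other causes, such as the disease itself. G-CSF is allowed during interruption and may shorten holds. Both limits stand.

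**Two stronger readings are tempting.** A reader might infer that a subject back at entry level will be scored as a DLT. The documents do not establish this: the interruption item is listed for Groups 1 and 2, its carry-over is only implied, and Sections 7.1.1 and 7.5 treat unchanged or baseline laboratory values as not requiring further action as adverse events, although neither section governs dosing. A reader might also fix one of the 6 subjects as a DLT and report the chance of a failed gate rising from 11% to 41% at a true rate of 10%. Any DLT from any cause gives that rise, so it does not measure this problem.

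**Conclusion.** The inconsistency is real and narrow. It rests on the printed Grade 3 limit and the Group 3 entry floor, and at the floor it needs no outside grading source. Its width above 1.0 × 10⁹/L is an assumption.

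If Table 6-2 governs, the continued hold and the loss of the same-dose option after 4 days follow directly. Discontinuation at 28 days is possible but not settled by the wording.

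The effect on the expansion gate runs from nil to the 0.33–0.43 shown above, depending on whether the interruption item applies and on assumed values of p and e. The documents support asking for that scope to be stated. They do not support saying that Group 3 subjects will be miscounted.

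**What to change.** Reconcile Section 3.2 (DLT list), Section 4.2 (criterion 8a), the Section 6.7.1 text and Table 6-2:

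- State for Group 3 whether a return to the subject's own entry ANC satisfies the recovery condition, and make table and text agree for all groups.
- Print the ANC grade limits that these rules use.
- State whether the interruption item of 7 days or more applies to Group 3, and define unresolved toxicity by the same recovery criterion.
- State whether the 28-day clause covers a first hematologic event.

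Which recovery rule is right is for the sponsor's clinicians.

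The cost is a phrase in Table 6-2, a phrase in the DLT list and short clarifications in 6.7.1, with no added procedures. SAP Section 1.3 records the study as completed with 33 subjects and does not give the Group 3 count. If any were in Group 3, the study report should say which reading was applied to their holds and DLT assessments.

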Dose escalation in Group 1 will continue until identification of the MTD, or a suitable lower recommended dose, for Phase II studies. At least 6 subjects should be treated and evaluated at the GS-5829 dose level recommended for Phase II studies.

A DLT in Group 1 or 2 is a toxicity defined below considered possibly related to GS-5829 occurring during the DLT assessment window (Study Day 1 through C1D28) in each cohort:

- Grade ≥ 4 neutropenia (absolute neutrophil count [ANC] $< 500/\text{mm}^3$)
- Grade ≥ 3 neutropenia (ANC $< 1000/\text{mm}^3$) with fever (a single temperature of $> 38.3^\circ\text{C}$ or a sustained temperature of $\geq 38^\circ\text{C}$ for more than one hour)
- Grade ≥ 3 thrombocytopenia
- Grade ≥ 2 bleeding (e.g. gastrointestinal, respiratory, epistaxis, purpura)
- Grade ≥ 3 or higher non-hematologic toxicity, except:
 - Grade 3 nausea or emesis with maximum duration of 48 hours on adequate medical therapy
- Grade 3 diarrhea which persists for < 72 hours in the absence of maximal medical therapy.
- Grade ≥ 2 non-hematologic treatment-emergent adverse event (TEAE) that in the opinion of the investigator is of potential clinical significance such that further dose escalation would expose subjects to unacceptable risk
- Treatment interruption of ≥ 7 days due to unresolved toxicity

For certain toxicities, such as laboratory assessments without a clear clinical correlate, a discussion between the investigator and medical monitor, may take place to determine if this adverse event (AE) should be assessed as a DLT necessitating dose reduction. However, any Grade 3 or Grade 4 elevation in AST or ALT associated with a Grade 2 elevation in bilirubin that is at least possibly related to study drug will be considered a DLT.

Group 3: For the first 6 subjects enrolled in the aggressive lymphoma group (Group 3), a modification of the DLT assessment for hematologic toxicity will be:

- Grade ≥ 4 neutropenia (absolute neutrophil count [ANC] $< 500/\text{mm}^3$) which persist for > 3 days upon interruption of GS-5829 (administration of growth factors not allowed concurrently, but allowed during GS-5829 interruption)
- Grade ≥ 4 thrombocytopenia ($< 25,000/\text{mm}^3$)
- Grade ≥ 3 thrombocytopenia ($< 50,000/\text{mm}^3$ to $25,000/\text{mm}^3$ which persists for > 7 days upon interruption of GS-5829)

Number of Subjects Planned:

Up to 160 subjects will be enrolled

Target Population:

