	Group 1 and 2: Non-lymphoma GS-5829	Group 3: Lymphoma GS-5829
NON-HEMATOLOGICAL ADVERSE EVENTS		
Hepatic Adverse Events (elevations in ALT, AST or bilirubin)		
Grade 1 (ALT/AST \leq 3xULN) (Bilirubin \leq 1.5xULN)	Maintain current dose level and schedule.	
Grade 2 (ALT/AST > 3-5xULN) (Bilirubin > 1.5 - \leq 3xULN)	Maintain current dose level and schedule. Monitor ALT, AST, ALP, and bilirubin at least 1x per week.	
Grade 3	Hold dosing until \leq grade 2. Permanently discontinue if any Grade 3 or Grade 4 elevation in AST or ALT associated with a Grade 2 elevation in bilirubin	
Grade 4	Permanently discontinue GS-5829	
Non hepatic, non-hematologic adverse events		
Grade \leq 2	No change in dosing required. Dosing may be interrupted until Grade \leq 1 or baseline	
Grade 3	Hold dosing until \leq grade 1 and decrease dose by at least one dose level and or by a change in schedule which decreases total GS-5829 administered over a 28 day dosing period	
Grade 4	Permanently discontinue GS-5829	

If the subject was not receiving GS-5829 at the time disease progression was documented (eg, due to reversible toxicity), after discussion with the Gilead Sciences Medical Monitor, GS-5829 may be re-started if the criteria for resuming treatment as described in Section 6.7.1 are met and the Investigator feels it is in the subject's best interest to do so.

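### Read literally, the hepatic rules hold dosing for Grade 3 AST/ALT with Grade 3 bilirubin but stop it permanently with Grade 2, and the DLT and Section 6.7.1 texts do not resolve this

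*Protocol*

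**What the plan says.** **Dosing, Table 6-2.** The hepatic rows cover rises in ALT, AST or bilirubin. The Grade 2 limits are printed as "ALT/AST > 3-5xULN) (Bilirubin > 1.5 - \leq 3xULN". The Grade 3 row opens with "Hold dosing until \leq grade 2" and then adds "Permanently discontinue if any Grade 3 or Grade 4 elevation in AST or ALT associated with a Grade 2 elevation in bilirubin". The Grade 4 row reads "Permanently discontinue GS-5829".

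**DLT definition, synopsis and Section 3.2.** A general bullet makes a DLT of Grade "3 or higher non-hematologic toxicity, except" for short-lived nausea or emesis and certain diarrhea. Liver tests are not among the exceptions. A later sentence lets the investigator and medical monitor discuss whether certain toxicities count; the example given is laboratory findings with no clear clinical correlate. One liver case, if judged possibly drug-related, is then declared a DLT outright: "any Grade 3 or Grade 4 elevation in AST or ALT associated with a Grade 2 elevation in bilirubin".

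**Section 6.7.1, text above the table.** For subjects without lymphoma, a DLT-type toxicity below Grade 4 means postponing GS-5829. Dosing may resume at least one dose level lower, after discussion with the medical monitor, if the toxicity returns to Grade 0-1 or baseline within 28 days. No hepatic exception is stated.

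**The concern.** A combined rise in transaminases and bilirubin is the case that the liver clause singles out, yet the clause names one bilirubin grade and not a minimum. A site that follows the words would stop treatment for good at the lower bilirubin grade and only hold it at the next one up, provided AST/ALT is Grade 3.

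The literal rule is also hard to apply over time. If a subject is held with both at Grade 3 and bilirubin improves first, the subject arrives at Grade 3 AST/ALT with Grade 2 bilirubin, which is the pair that triggers permanent discontinuation.

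DLT incidence is the primary endpoint (Section 8.1.2), and in Group 1 fewer than 2 DLTs in up to 6 subjects opens the next level. Which liver events are DLTs without discussion therefore bears on escalation as well as on individual safety.

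**Working it through.** No power or sample-size figure is involved. The check applies the printed rules to each combination.

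**Inputs.** From Table 6-2, Grade 2 ends at 5 x ULN for AST/ALT and at 3 x ULN for bilirubin, so a bilirubin above 3 x ULN is not Grade 2. The table prints no numeric limits for Grades 3 and 4. The DLT rules are those of the synopsis and Section 3.2. In the table below, DLT by default assumes that the event is possibly related and within the window.

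| AST/ALT | Bilirubin | Table 6-2 instruction | DLT status |
|---|---|---|---|
| 3 | 0 or 1 | Hold until Grade 2 or lower | By default; discussion open |
| 3 | 2 | Permanent stop (clause in Grade 3 row) | Declared outright |
| 3 | 3 | **Hold until Grade 2 or lower** | By default; discussion open |
| 3 | 4 | Permanent stop (Grade 4 row) | By default; discussion open |
| 4 | 0 or 1 | Permanent stop (Grade 4 row) | By default; discussion open |
| 4 | 2 | Permanent stop | Declared outright |
| 4 | 3 or 4 | Permanent stop (Grade 4 row) | By default; discussion open |

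**Dosing.** There are 2 x 5 = 10 combinations. The instruction becomes milder as bilirubin worsens in one of them: AST/ALT Grade 3 with bilirubin Grade 3. As a test of how much hangs on the wording, reading Grade 2 as Grade 2 or higher changes the dosing instruction in that one combination and nowhere else.

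**DLT.** The outright declaration is absent in 2 x 2 = 4 combinations with worse bilirubin (AST/ALT Grade 3 or 4 with bilirubin Grade 3 or 4). All 4 remain DLTs by default under the general Grade 3 bullet.

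**Text against table, subjects without lymphoma.**

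- Grade 3 AST/ALT with Grade 2 bilirubin is a DLT below Grade 4. The text of Section 6.7.1 permits conditional resumption; Table 6-2 requires a permanent stop.
- Where Table 6-2 holds dosing for a Grade 3 liver event, its recovery level is Grade 2 or lower. The text of Section 6.7.1 requires Grade 0-1 or baseline.

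**Is a minimum implied elsewhere?** The same DLT lists print a greater-or-equal sign where a minimum is meant, for example for bleeding and thrombocytopenia. The liver sentence spells out two grades for AST/ALT and one for bilirubin, and does so in all three places, so a symbol lost in text extraction is unlikely. The liver categories in SAP Section 7.2.3 set bilirubin thresholds with no upper limit. Grade 2 may have been meant as a floor, but neither document says so.

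**The case against.** The strongest reply is that the gap is small and well surrounded. Grade 4 in either measure is already a permanent stop. Grade 3 or higher liver toxicity is already a DLT, and so is an interruption of 7 days or more for unresolved toxicity. The discussion is optional and is described for laboratory findings without a clear clinical correlate, which a joint rise in transaminases and bilirubin need not be. Section 6.7 presents its rules as guidelines, restart is never compulsory, and Section 3.4 allows the investigator to stop for toxicity. All of this stands, and it limits the point to what is stated here.

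A reader might go further and infer that any worse bilirubin permits restart, or that these events are simply negotiable as DLTs. The documents do not support either. The Grade 4 row closes off restart for Grade 4 bilirubin, and the default DLT bullet applies to all four combinations. A reader might also picture one reclassified subject turning 2 of 6 DLTs into 1 of 6 and so opening the next level. That would need this exact laboratory pair, a discussion that overturns the default, and exactly one other DLT at the level. The documents give no frequency for any of these. In Group 2, escalation rests on a Bayesian model and the safety review team, not on that count.

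Section 6.7.1 cannot be used to show milder handling of worse bilirubin either, because its resumption text covers the Grade 2 bilirubin case too. It shows a separate conflict between text and table.

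None of this explains why the written instruction is stricter at bilirubin Grade 2 than at Grade 3.

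**Conclusion.** The point holds in a narrow form. As written, the dosing rule inverts in one combination of ten: AST/ALT Grade 3 with bilirubin above 3 x ULN but short of Grade 4. The upper end of that range is not printed in the protocol, which only links to CTCAE v4.03. For DLTs, four combinations with worse bilirubin lack the express exclusion from discussion that the Grade 2 combination has, though all four are DLTs by default. Separately, the text of Section 6.7.1 and Table 6-2 disagree on stopping and on recovery level for subjects without lymphoma.

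This rests on taking Grade 2 at its printed limits. If the sponsor meant a minimum, the defect is one of wording, but the wording is what sites apply. SAP Section 1.3 reports 33 subjects enrolled at completion, and the documents do not show whether such a case arose. An event judged not to be a DLT would be absent from the DLT listing (SAP Section 7.1.7.1), although the liver summaries and listing of SAP Section 7.2.3 should still show the laboratory values. A stopping rule in a first-in-human study that inverts when followed literally needs correction, even at this size.

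**What to change.** Reconcile four places: the DLT definition in the synopsis, the same definition in Section 3.2, the text of Section 6.7.1, and the hepatic rows of Table 6-2. In the same words in each place, state which bilirubin grades the permanent-stop and outright-DLT clauses cover, and which recovery level applies before dosing may resume. The Section 6.7.1 text has to be included, because aligning only the other three would leave the conflict with the table in place. Which grades and which recovery level are right is for the sponsor to decide.

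The cost is a wording change in four places. It needs no new data, procedures or subjects.
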